7. ASSESSMENTS

7.1 Safety Assessment

The measures of safety used in this study are based on previous study data. They include a close vigilance for, and stringent reporting of selected local and systemic adverse events routinely monitored in vaccine studies as indicators of reactogenicity.

An adverse event (AE) is defined as any untoward medical occurrence in a subject or clinical investigation subject administered a pharmaceutical product at any dose that does not necessarily have to have a causal relationship with this treatment. Therefore, an AE can be any unfavorable and unintended sign (including an abnormal laboratory finding, for example), symptom, or disease temporally associated with the use of an investigational product, whether or not considered related to the investigational product. This definition includes intercurrent illnesses or injuries and exacerbation of pre-existing conditions.

The period of observation for AEs extends from the time the subject signs informed consent until he or she completes the specified safety follow-up period (28 days after each vaccination) or terminates the study early (whichever comes first). AEs occurring after the informed consent form is signed but prior to receiving study vaccine/product will be documented as an adverse event and recorded within source document. However, any AEs occurring prior to receipt of any study vaccine will be analyzed separately from “treatment emergent” AEs (AEs occurring after administration of the first study vaccine).

Adverse events are collected as either solicited or unsolicited adverse events. Solicited events are derived from organized data collection systems, such as Subject interview.

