8.4.2.1.3 Analysis of Unsolicited Adverse Events

This analysis applies to all adverse events occurring during the study, judged either as probably related, possibly related, or not related to vaccination by the investigator, recorded in AE CRF, with a start date on or after the date of first vaccination. AE starting prior to the first vaccination will only be listed. The original verbatim terms used by

investigators to identify adverse events in the CRFs will be mapped to preferred terms using the MedDRA dictionary. The adverse events will then be grouped by MedDRA preferred terms into frequency tables according to system organ class (SOC).

All reported adverse events, as well as adverse events judged by the investigator as at least possibly related to study vaccine, will be summarized according to SOC and preferred term within SOC. These summaries will be presented by vaccination group. When an adverse event occurs more than once for a subject, the maximal severity and strongest relationship to the vaccine group will be counted.

Separate summaries will be produced for the following categories:

- Serious adverse events and adverse events of special interest.
- Adverse events that are possibly or probably related to vaccine.
- Adverse event leading to withdrawal.

Data listings of all adverse events will be provided by subject. In addition, adverse events in the categories above will be provided as listed data.

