8.8 Derived and Computed Variables

Demographics

Age will be calculated in years using the following formula:

$$(\text{Date of Visit 1} - \text{Date of Birth} + 1) / 365.25$$

Body Mass Index (kg/m²) will be calculated using the following formula:

$$\text{Weight (kg)} / \text{Height}^2 (\text{m}^2)$$

Immunogenicity

Values below the limit of quantification (recorded as “< LQ”) will be set to half that limit (i.e., LQ/2].

Seroresponse is defined for subjects with non-missing values pre-vaccination and post-vaccination as:

If the baseline value is greater than 50 EU then an increase of at least 50% in the post-vaccination sample as compared to baseline [i.e. $((\text{Post-vac minus baseline})/\text{baseline})100\% \geq 50\%$]

If the baseline value is less or equal to 50 EU then an increase of at least 25 EU in the post-vaccination sample as compared to baseline [i.e. $(\text{post-vac minus baseline}) \geq 25 \text{ EU}$]

High seroresponse is defined for subjects with non-missing post-vaccination as:

Post vaccination titer ≥ 121 anti-LPS serum IgG units in the GSK ELISA

Geometric Mean Concentration

The GMC will be calculated using the following formula:

$$10^{\left\{ \frac{\sum_{i=1}^n \log_{10}(t_i)}{n} \right\}}$$

where t_1, t_2, \dots, t_n are n observed immunogenicity titers/concentrations.

Geometric Mean Ratio

Geometric mean ratios (GMRs) measure the changes in immunogenicity titers/concentrations *within* subjects.

The GMR will be calculated using the following formula:

$$10^{\left\{ \frac{\sum_{i=1}^n \log_{10}\left(\frac{v_{ij}}{v_{ik}}\right)}{n} \right\}} = 10^{\left\{ \frac{\sum_{i=1}^n \log_{10}(v_{ij}) - \log_{10}(v_{ik})}{n} \right\}}$$

where, for n subjects, v_{ij} and v_{ik} are observed immunogenicity titers/concentrations for subject i at time-points j and k , $j \neq k$.

Duration in the Study

Duration in the study is defined in days as:

Last visit date (visit x)^a – Enrollment date (visit 1) + 1

^aor premature discontinuation date (in case of withdrawal from the study)

The duration is missing if one of the dates is missing or incomplete.

Solicited Adverse Events

For details see [section 13.2](#).

Unsolicited Adverse Events

All adverse events will be characterized according to the date of occurrence related to the vaccination phase as follows:

- **Emergence before vaccination phase:** start date before the first date of injection of study vaccine.

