- **Emergence during vaccination phase:** start date on or after the first date of injection of study vaccine or, adverse event increase in severity including to “serious” adverse event.

If start date is equal to the first date of injection then “timing” variable (“On injection day, before injection”/“On injection day, after injection”) will be used to define whether the adverse event occur before or after the injection.

If there are several vaccinations, the adverse event will be associated with the most recent vaccination.

If an adverse event start date is missing or unknown, the adverse event will be considered as emergent.

When start and/or end dates of an adverse event are only partially known, adverse events will be categorized as emergent before, during, or after vaccination phase using the following rules:

- If the partial end date is before ($<$) the first study vaccination (i.e., year or year & month is/are before the first study vaccination year or year & month) then the adverse event is emergent before vaccination phase.
- If the partial start date is equal or after (\geq) the first study vaccination (i.e., year or year & month is/are after or the same as the first study injection year or year & month) then the adverse event is emergent during vaccination phase.

The **maximum event severity** is the greatest severity associated with a preferred term for a reported adverse event according to the following order: Mild < Moderate < Severe. Unknown/ Missing severity is considered as severe (except for the definition of emergence).

Multiple AEs with the same PT for the same subject are counted only once.

Vaccination-related Adverse Events are those for which the cause has been evaluated by the investigator, and recorded either as possibly related, probably related or unknown/missing.

Safety Laboratory Data

All laboratory measurements summarized in the CSR are those defined in the study protocol.

Reference ranges used to categorize the results as “low” (values below the lower limit of the reference range), “normal” (values within the reference range) or “high” (values above the upper value of the reference range) will be those provided by the site lab which performed the tests and provided the laboratory reports.

Prestudy, Concomitant and Post-Vaccination Medications

A **previous medication** is a medication used only before the first study vaccination (i.e. medication end date < first study vaccination date).

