13.3 Unsolicited Adverse Events

All AEs occurring during the first 28 days after each vaccination, including the day of vaccination, and all AEs leading to withdrawal, all SAEs and all AEs of special interest occurring at any time during the study will be recorded according to the protocol-specified reporting rules.

The original verbatim terms used by investigators to identify adverse events in the CRFs will be mapped to preferred terms using the MedDRA dictionary. The unsolicited adverse events will then be grouped by MedDRA preferred terms into frequency tables according to system organ class. Adverse events judged by the investigator as at least possibly related to study vaccine will be summarized by vaccine group, according to system organ class and preferred term within system organ class. When an unsolicited adverse event occurs more than once for a subject, the maximal severity and strongest relationship to the vaccine group will be counted.

Only vaccine-emergent adverse events (see [section 8.7](#) for definition) will be analyzed, i.e., excluding those after a subject has given informed consent but before vaccination. The selection of unsolicited adverse events and the assignment to time intervals will be done by day of onset and not by days ongoing/persisting.

The summaries will be presented by period of onset and will include frequency distributions of the different adverse events:

- Onset between day 1 and study termination.

The analysis of unsolicited adverse events comprises the following categories:

- Any unsolicited adverse event.
- Possibly or probably related unsolicited adverse events.
- Unsolicited adverse events leading to death.
- Serious adverse events.
- Possibly or probably related serious adverse event.
- Unsolicited adverse events leading to premature withdrawal from study.

- Unsolicited adverse events leading to dose reduction, interruption or delay in study vaccination.
- Unsolicited adverse events leading to hospitalization.

Solicited adverse events continuing beyond day 7 will be coded by MedDRA and combined with the respective unsolicited adverse events.

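### Protocol 8.4.2.1.3, SAP 8.8 and SAP 13.3 disagree on whether an adverse event that begins before dose 1 and worsens after it counts in primary endpoints (c) and (d)

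*SAP*

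**What the plan says.** Three places decide which unsolicited events are summarised.

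- **Protocol 8.4.2.1.3** applies the analysis to events "with a start date on or after the date of first vaccination" and adds that "AE starting prior to the first vaccination will only be listed". It makes no exception for worsening. The summary of serious events and events of special interest is produced under the same section.
- **SAP 8.8 (Unsolicited Adverse Events)** has two categories. An event is emergent before the vaccination phase if it has a "start date before the first date of injection of study vaccine". It is emergent during that phase if it has a "start date on or after the first date of injection of study vaccine or, adverse event increase in severity", and the text goes on to include a change to serious.
- **SAP 13.3** restricts the analysis to vaccine-emergent events, which it explains as "excluding those after a subject has given informed consent but before vaccination". It then states: "The selection of unsolicited adverse events and the assignment to time intervals will be done by day of onset and not by days ongoing/persisting". For the definition it points to SAP 8.7, which is Data Transformation; the definition is in SAP 8.8.

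The endpoints concerned are in Protocol 8.1.1.1: (c) subjects with unsolicited adverse events in the 28 days after each vaccination, and (d) subjects with serious adverse events over the whole study. Neither carries a start-date restriction tied to first vaccination.

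**The concern.** Adverse events are observed from signed consent (Protocol 7.1), and screening can take place up to 28 days before Visit 1 (Protocol 3.1). A subject can therefore have a recorded mild event at dose 1 that becomes severe or serious afterwards. A safety study would normally want that in its summaries. Whether it gets there depends on which of the three passages the programmer follows, and nothing says which prevails.

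Safety is the only primary objective and the arms are small, so one subject is visible in a table. If the rule is still open when treatment codes are released, it could be chosen with the affected events and their arms in view.

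**Working it through.** **The plan's own design figures.** The protocol synopsis states an 87% chance of at least one event per group, with 20 evaluable subjects and a true rate of 10%. Check: 1 − 0.9^20 = 0.878, which agrees. For 15% dropout, 20 / 0.85 = 23.5, rounded up to 24 per group, which also agrees. The point below does not depend on either figure.

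**One event put through each rule.** Take an event that starts after consent, is mild at dose 1, becomes severe or serious after dose 1, and stays on one record with its pre-dose start date.

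1. Protocol 8.4.2.1.3: the start date precedes first vaccination, so the event is listed and not summarised.
2. SAP 8.8, during-vaccination category: the severity increased, so the event is emergent. This limb does something only for events that began before first injection, because later ones already qualify by start date. It looks deliberate: the same section treats missing severity as severe, but not when emergence is being defined.
3. SAP 8.8, before-vaccination category: the start date precedes first injection, so the event qualifies here too. The two categories overlap for exactly this event, and no priority is given.
4. SAP 13.3: by its reference to emergent events the event is in; by its explanation and its selection by onset day the event is out. The cross-reference leads to the wrong section, so it does not settle the matter.

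SAP 8.8 does not say that the increase must follow dose 1. That is the natural reading, since the limb sits under the vaccination phase, and it is assumed here.

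**Size.** The documents give no rate of pre-dose events that worsen, so only the effect per subject can be stated.

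- One reclassified subject, all 24 in the denominator: 1/24 = 4.2 points. With 20 in the denominator: 1/20 = 5.0 points.
- Endpoint (c) counts subjects with any unsolicited event. If the subject already has another qualifying post-dose event, the change is 0, so 1/24 is a ceiling.
- Endpoint (d), with no other serious event in the arm: 0/24 = 0% (Clopper-Pearson 95% interval 0 to 14.2%) becomes 1/24 = 4.2% (0.1 to 21.1%). The intervals are added here to show scale.

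**The case against.** The strongest reply is that the protocol already provides for worsening. Its definition of an adverse event in 7.1 includes exacerbation of pre-existing conditions, so a site may enter the worsening as a new event with a post-dose start date. That record passes all three rules and the conflict has no effect. This stands as a qualification. But no passage requires a new record, so the counts would depend on site practice.

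It can also be said that the onset sentence in SAP 13.3 contrasts onset with persistence, and so may concern only the assignment of events to intervals. That is a fair reading of the sentence alone. It does not remove the explanation beside it, which excludes events before vaccination.

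Three stronger readings are tempting, and the documents do not support them.

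- *Serious events would be missed.* They would not. Protocol 7.1.5 requires every serious event during the study to be reported and entered on the Adverse Events CRF. Only its place in the summary tables is uncertain.
- *Pre-dose events never reach the CRF, so the SAP 8.8 rule has no baseline severity.* Protocol 7.1 does say that such an event "will be documented as an adverse event and recorded within source document", and Table 2 begins adverse event assessment at Visit 1. But Protocol 9.1 makes source recording a step before CRF entry, Protocol 10.1 puts all clinical data on CRFs, Protocol 8.4.2.1.3 plans to list these events, and SAP 8.8 has a timing variable that covers events on the injection day before injection.
- *An expected shift per arm can be calculated.* That needs the proportion of subjects with an ongoing event at dose 1 and the proportion who worsen. The documents give neither, and the subjects are screened for good health.

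Finally, the study is descriptive, tests no hypothesis, and would apply any one rule alike to all arms. That is correct. It limits the consequence to the completeness and reproducibility of the counts.

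**Conclusion.** The inconsistency is in the current text and should be resolved before unblinding. SAP 8.8 counts a pre-dose event that worsens or turns serious after dose 1; Protocol 8.4.2.1.3 and the wording of SAP 13.3 only list it. SAP 8.8 also places the event in both of its own categories.

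The effect is possible, not certain. It needs at least one such event, kept on its original record. Each affected subject then moves an arm by at most 4.2 points with 24 in the denominator, and endpoint (c) may not move at all. The change would show most in endpoint (d), where an arm could read 0/24 or 1/24 by choice of rule. This is a matter of consistent counting. It does not imply biased comparison between arms, lost safety reports or an inadequate sample size.

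**What to change.** Before unblinding, put one emergence rule in SAP 8.8, SAP 13.3 and Protocol 8.4.2.1.3. An unsolicited event is emergent if it starts after first injection, or if it started earlier and increased in severity or became serious after first injection. In the second case the date of worsening is the onset date, so that selection by onset day in SAP 13.3 works unchanged.

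The edits that follow are:

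- In SAP 8.8, limit the before-vaccination category to events that do not worsen after first injection.
- In SAP 13.3, bring the explanation of emergent events into line and correct the cross-reference from 8.7 to 8.8.
- In Protocol 8.4.2.1.3, replace the listing sentence with wording such as: *AEs that began before first vaccination and did not worsen after it are listed only.*

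The SAP edits are changes of wording. The protocol edit needs an amendment approved by the sponsor and the IRB/EC, and by health authorities where required (Protocol 13.4). Event counts may be slightly higher than under the protocol's present rule.

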All other medications are **concomitant**.

When start and/or end dates of a medication intake are missing, the medication is considered as concomitant with the study vaccination schedule.

If the first study vaccination date is missing then the medication is considered as concomitant with the study vaccination schedule, provided that the study vaccine was administered to the subject.

For further details please refer to the technical and program specifications document stored in Home/analysis/H03_01TP/final/prod/docs within the SAS Drug Development (SDD) server.

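### SAP 8.8 does not check for a complete end date before dose 1, so an adverse event already over can be classed as vaccine-emergent; some date patterns get contradictory answers (minor)

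*SAP*

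**What the plan says.** SAP 8.8 calls an event pre-vaccination if it starts before the first injection, and emergent if it starts on or after that date or worsens. It then adds rules for incomplete dates:

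- Start date absent: "If an adverse event start date is missing or unknown, the adverse event will be considered as emergent".
- Partial end date in a year or month before the first vaccination: "then the adverse event is emergent before vaccination phase".
- Partial start date: the event is emergent if the "year or year & month is/are after or the same as the first study injection year or year & month".

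For medications, the same section defines a previous medication by an end date before the first study vaccination. It then states: "When start and/or end dates of a medication intake are missing, the medication is considered as concomitant with the study vaccination schedule".

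Elsewhere the plan keeps pre-vaccination events apart. Protocol 7.1 says "AEs occurring after the informed consent form is signed but prior to receiving study vaccine/product will be documented as an adverse event" and has such events analysed separately from treatment-emergent ones. Protocol 8.4.2.1.3 says "AE starting prior to the first vaccination will only be listed". SAP 13.3 limits the analysis of unsolicited events to vaccine-emergent ones and leaves out those between consent and vaccination.

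**The concern.** An event that ended before the first injection must also have started before it, and it cannot have worsened afterwards. Its class is therefore known even when the start date is not. SAP 8.8 uses an end date for adverse events only when that date is partial and falls in an earlier month or year. A complete end date, which is the better information, is never consulted.

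Safety is the primary objective, and primary endpoint (c) counts subjects with unsolicited adverse events after each vaccination. With 24 subjects per arm, one illness that was over before vaccination could show in a table row. Where two rules disagree, the result also depends on which condition the programmer happens to code first.

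**Working it through.** The plan states no figure on this point, so the check is to apply the rules literally. The first-injection date of 20 October 2016 is assumed for illustration.

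| Start | End | Rule that applies | Class under SAP 8.8 | Class shown by the dates |
|---|---|---|---|---|
| missing | 8 Oct 2016 | missing start | emergent | before |
| missing | 28 Sep 2016 | missing start | emergent | before |
| Oct 2016 | 8 Oct 2016 | partial start, same month | emergent | before |
| 2016 | 28 Sep 2016 | partial start, same year | emergent | before |
| missing | Sep 2016 | missing start; partial end | emergent and before | before |
| 2016 | Sep 2016 | partial start; partial end | emergent and before | before |
| Sep 2016 | 8 Oct 2016 | basic definition | before | before |
| 5 Oct 2016 | 8 Oct 2016 | basic definition | before | before |
| missing | Oct 2016 | missing start | emergent | not determined |

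The first four rows are wrong, and no competing rule rescues them. The next two rows are contradictory. The seventh row shows the limit of the problem: a start month earlier than the month of dose 1 is classed correctly. In the last row the end date does not settle the question, so the emergent default is reasonable.

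Medications: take a missing start and an end of 8 October 2016. The definition makes the drug previous, because its end date precedes the first vaccination. The missing-date rule makes it concomitant, because a missing start alone is enough to trigger it. No precedence is stated.

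Can such records arise? Protocol 7.1 observes adverse events from consent, and screening runs from Day -28 to Day -1 (Protocol 3.1). Protocol 6.5 records medications from the 4 weeks before the study. So they can arise, but the documents give no count of incomplete dates.

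Size per record: 1/24 = 4.2 percentage points on an arm of 24. If the denominator were the 20 evaluable subjects of the synopsis, it would be 1/20 = 5.0 points. Either figure applies only to a subject with no other counted event in that row, because SAP 8.8 counts repeats of one preferred term once per subject.

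**The case against.** Counting an event with an unknown start as emergent is a usual conservative choice. The trial is descriptive and tests no hypothesis, and the randomised vaccine cannot have caused a pre-dose event. Incomplete dates can be queried (Protocol 10.2). Protocol 7.1 speaks of recording pre-dose events in the source document, and the synopsis collects events on the CRF from Visit 1, so few may reach the database. All of this limits the effect. It does not justify the rule where the end date removes the uncertainty, and both Protocol 8.4.2.1.3 and SAP 8.8 expect pre-dose events to be handled in the analysis.

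Precedence might be settled in the programming specification that SAP 8.8 cites. Its path names another study, H03_01TP, so the documents do not show that it is.

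A reader might infer more than the documents support:

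- **That about half of the pre-dose events with a month-only start are misclassified.** If onsets are uniform over days 1 to 28 before dose 1, the share in the month of dose 1 is about 1 - 14.5/30.44 = 0.52. That is a share of all pre-dose onsets, not of events known to have ended. With an assumed 7 days from onset to end, onsets lie 8 to 28 days before dose 1 and the share is 1 - 18/30.44 = 0.41. Neither figure says how many dates are incomplete.
- **That every event with a missing start and a pre-dose end becomes emergent.** With a partial end date in an earlier month the rules conflict, so the answer is undefined.
- **That the antipyretic results are affected.** Post-vaccination use comes from the diary card and is summarised for 30 minutes to day 7 (SAP 13.2). The medication conflict reaches only the descriptive table in SAP 13.6.
- **That the serious-event endpoint is materially exposed.** Serious events go on a separate form and are reported within 24 hours (Protocol 7.1.4 and 7.1.5). Nothing suggests that their start dates would be missing.

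**Conclusion.** Wrong as written; minor severity. Followed literally, SAP 8.8 classes as emergent an adverse event that a complete end date shows was over before dose 1. This happens when the start is missing, or is partial and in the same month (or, if only the year is known, the same year) as dose 1. For a missing or year-only start with a partial end in an earlier month, and for drugs with a missing start and a pre-dose end, the rules contradict each other. This goes against Protocol 7.1 and 8.4.2.1.3 and SAP 13.3.

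The effect is at most 4.2 points per wrongly counted subject on an arm of 24, provided that the subject has no other counted event in the row. The number of such subjects is not given and may be zero. The conclusion rests on reading 8.8 as printed, without the cited specification.

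**What to change.** Put the end-date check first in SAP 8.8:

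*If the end date, complete or partial, shows that the event ended before the first injection, the adverse event is before the vaccination phase whatever the start date; only otherwise does a missing or same-period partial start date count as emergent.*

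For medications:

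*If the start date is missing, classify by end date; treat as concomitant only if the end date is missing or not before the first vaccination.*

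The cost is two sentences in the SAP and one reordered condition in each derivation. Data collection does not change. The edit should be made before unblinding, so that no class depends on a choice made with the allocation known.
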